#### **Project Summary**

The multi-disciplinary UPMC Post-COVID Recovery clinic serves the clinical needs of Long-COVID patients, those with persistent symptoms after initial infection recovery. Using an IRB-approved research registry collecting biomarkers, clinical data, imaging results and patient-reported outcomes (PROs), this group defines burden of long-COVID and guides personalized medicine strategies.

To date, phenotyping of 148 Long-COVID patients show 86% with new onset cognitive fog (using validated criteria) and 48% with depression (PHQ8 criteria). Cognitive fog was the most common complaint endorsed by patients during their clinic evaluations. ***Additionally, a subgroup of patients requesting a behavioral evaluation, who were in the prime of their adult productivity, reported that "cognitive fog" was the main symptom impacting their functioning, work performance, and life satisfaction; making it a critical domain to target clinically.*** The specific cognitive deficits reported as part of this "fog" varied across patients.

In a pilot study, we prescribed 90 of these depressed patients a coached digital cognitive behavioral therapy (dCBT) app developed by UPMC called RxWell, as part of care. Half of the patients (N = 45) downloaded the app and the 75% who completed techniques showed improvement in depression over 3 months (large effect size of change with PHQ8 (delta 6; p=0.001; Cohen's d=1.1; mean age 46)).

We posit rapid, accurate, and scalable assessment of cognitive impairment and implementation of the right interventions targeting specific deficits is a better fuller recovery path for these patients. ***This proposal evaluates the utility of computer-based evaluation of COVID-related cognitive fog and the relative efficacy of two intervention strategies to treat moderate cognitive impairment using a randomized trial which will inform the design of a future adaptive trial.*** We plan to study 120 post-COVID patients seen in the Long-COVID clinic over the next 12 months with moderate or severe cognitive fog to assess the type and severity of neurocognitive impairment using computerized neuropsychological testing (BrainCheck). We will randomize to either 1) dCBT with coaching (RxWell) versus 2) stimulant medication (amphetamine/dextroamphetamine), as part of the study embedded in clinical care, to provide data to inform design of future larger phase adaptive trials. BrainCheck is

an FDA-approved technology to provide rapid, mobile cognitive assessment with venture investment and partnership with UPMC Enterprises. RxWell is a mobile app, developed and housed at UPMC Health Plan, with health coaches employed by UPMC. Both technology solutions improve access in an era of shortage of neuropsychologists and mental health providers. Stimulants have documented safety and effectiveness in helping neurocognitive deficits in conditions with similar deficit such as ADHD, post-concussion, and other inflammatory medical conditions.

We will evaluate effects of treatments on **cognitive impairment (primary aim)** and emotional distress (depression), satisfaction with life, work disability and health care utilization (secondary outcomes) over 3 months. Findings will provide inform and guide the design for the next phase adaptive clinical trial. These results will be generalizable to treating other common neuroinflammatory cognitive deficits such as that which follows ICU admission for sepsis or respiratory failure or following chemotherapy.

#### **Select the item(s) that best support(s) your research**

- ✓ **Promotes research with new approaches and innovations in care.**
- ✓ Incorporates the concept of comparative effectiveness and/or embedded and **adaptive designs**, which allows researchers to rapidly test multiple treatment approaches more efficiently than traditional clinical trials and with quicker, more applicable results.
- ✓ Supports a current UPMC focused initiative, including (but not limited to) those with aggressive approaches to cancer, gastrointestinal, heart disease **and neuroscience**.

**Problem statement:** (COVID-19 threatened the health of millions of Americans and others across the globe. After acute illness, prolonged effects called Long-COVID extract much from sufferers; data driven methods to address and manage these symptoms are lacking. Cognitive fog and emotional distress are common longer-term consequences after COVID-19. In our clinic, 80% of Long-COVID patients report persistent cognitive fog and 46% of these have at least moderate depressive severity. Both inflammatory and non-inflammatory factors may cause the cognitive and depressive symptoms.

We propose two efficient solutions that advance the treatment of reversible cognitive impairment secondary to COVID, which may apply to other medical conditions. ***Our two interventions approach the problem from different perspectives- one targeting cognitive fog associated with depression, the other the cognitive fog directly.*** For depression with cognitive fog, a digital cognitive behavioral solution with health coaches offers cognitive rehabilitation strategies. For cognitive fog without depression, a stimulant medication known to reduce cognitive impairment in other chronic medical conditions will be used. Preliminary findings from this project will provide the necessary data to write a competitive federally supported proposal to fund a larger-scale adaptive design study. This next phase proposal will also incorporate learnings from this preliminary study to personalize intervention strategies to target specific cognitive domains of impairment. We will seek both federal funding and internal funding (UPMC Enterprises) for this next larger phase.

#### **Summary of Project**

Design Summary: Randomized trial of dCBT versus stimulant to treat cognitive impairment +/- depression in adults with Long-COVID.

Aim 1: Test efficacy of two interventions for improving cognitive impairment (primary outcome) and emotional distress (depression), life satisfaction, work disability, and medical utilization (secondary

outcomes). Assess effect of demographic and COVID symptom characterization variables on treatment efficacy.

Hypothesis: Stimulant therapy will outperform dCBT for patients with cognitive impairment alone and dCBT will outperform stimulant for cognitive impairment and depression.

Aim 2: Define the important response characteristics in these patients to inform design of a larger adaptive clinical trial evaluating treatment options for COVID-related cognitive impairment.

Methodology: Participants with confirmed Long-COVID cognitive impairment assigned with a 1:1 allocation to either arm using a permuted block design stratified by depression severity. Participants will complete computerized neurocognitive assessments and other study measures at baseline, 1.5 (interim) and 3 months after randomization.

Inclusion: Patients with Long-COVID between ages of 21-65; moderate cognitive impairment (MOCA $\leq$ 18) present for at least 3 months; access to a smartphone.

Exclusion: No history of dementia, psychosis, mania, addiction or current conditions requiring immediate hospitalization. No history of stimulant failure. No current cardiac condition

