#### **Interventions:**

1. RxWell is a mobile application that consists of CBT techniques and a health coach who provides in-app guidance and risk mitigation. Coaches will receive training to provide cognitive rehabilitation tips. Usage will be tracked.
2. Standardized dosing of amphetamine/dextroamphetamine monitored monthly with response-based titration to maximum dose of 20 mg bid with side effects tracked. To date, patients with post-COVID fog have tolerated stimulants well.

Clinical flow and recruitment rates for registry study make 12-month recruitment completion feasible.

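### Does excluding prior stimulant failure, with no matching rule or baseline record for prior RxWell use, distort the comparison of the two arms?

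*Combined protocol and SAP*

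**What the plan says.** Under Summary of Project, the exclusions include "No history of stimulant failure". None of the criteria mentions RxWell, dCBT or CBT; the only one tied to the app is smartphone access. Randomisation is 1:1, stratified by depression severity.

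The Project Summary describes a pilot in the same clinic: "we prescribed 90 of these depressed patients a coached digital cognitive behavioral therapy (dCBT) app". It continues "Half of the patients (N = 45) downloaded the app", and "the 75% who completed techniques showed improvement in depression over 3 months". For the trial itself it says "We plan to study 120 post-COVID patients seen in the Long-COVID clinic over the next 12 months".

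Under Interventions, the remark "To date, patients with post-COVID fog have tolerated stimulants well" implies that some patients with this condition have already taken a stimulant. The sentence there on tracking usage concerns the app as a trial intervention, not history before entry.

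The Statistical Analysis section specifies intent-to-treat analyses stratified by depression severity. The models contain assigned arm, depression severity, the baseline score and, in multivariable versions, demographic and COVID symptom covariates. Prior treatment is not named.

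**The concern.** Prior history is screened for one treatment and not for the other. Patients known to have failed a stimulant stay out. Patients who tolerated a stimulant, and patients who were offered RxWell and did not take it up or benefit, could all enter. The documented RxWell exposure lies in depressed patients, which is where the Aim 1 hypothesis expects dCBT to win. If many such patients enrolled and responded less the second time, the dCBT contrast in that stratum would shrink. The smaller effect would then pass into the Aim 2 simulations and the decision on which interventions move to Phase 3. With no baseline record, a reader could not see how many patients had already used, or declined, the treatment assigned to them.

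**Working it through.** **1. The plan's own figures.** 45/90 = 0.50, as stated. 75% of 45 = 33.75, about 34 completers. One base does not reconcile: 48% of the 148 phenotyped patients is 71, fewer than the 90 depressed patients prescribed the app. The counts are used below only as an indication of scale.

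**2. Size of the stratum.** The problem statement says "46% of these have at least moderate depressive severity"; the Project Summary gives 48%. 0.46 × 120 = 55.2 and 0.48 × 120 = 57.6. Take n = 56.

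**3. Possible shift.** The documents give neither the exposed share *f* nor the share of effect lost *s*. Assume a 0.5 SD dCBT advantage in patients new to the app, f = 10-25% and s = 50-100%. Shift = f × s × 0.5. Unadjusted SE of the contrast = sqrt(4/56) = 0.267 SD.

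| f | s | shift (SD) | shift / SE |
|---|---|---|---|
| 10% | 50% | 0.025 | 0.09 |
| 10% | 100% | 0.050 | 0.19 |
| 25% | 50% | 0.0625 | 0.23 |
| 25% | 100% | 0.125 | 0.47 |

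If no pilot patient enrols, f = 0 and so is the shift. The other extreme, all 45 downloaders enrolling, gives 45/57.6 = 78% to 45/55.2 = 82% of the stratum; nothing in the documents suggests it.

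**4. Direction.** Suppose the 0.5 SD arises only in downloaders and half of new patients download, as in the pilot. Downloaders then gain 0.5/0.5 = 1.0 SD. If earlier behaviour repeats, the effect in exposed patients is p × g × 1.0, where p is the share of them who downloaded before and g the share of the gain kept.

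- p = 0.5, g = 1: 0.5, no change.
- p = 0.5, g = 0.5: 0.25, so s = 50%.
- The 34 completers stay out: 90 − 34 = 56 remain, of whom 45 (80%) never downloaded. With p = 0.2, g = 1 the effect is 0.2, a loss of 0.3 × f = 0.03-0.075 SD.
- p = 0.75, g = 1: 0.75, so the contrast rises by 0.25 × f = 0.025-0.0625 SD.

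The sign is therefore not determined.

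**5. Would an analysis of unexposed patients do better?** Take the effect in unexposed patients as the target. The intent-to-treat RMSE is sqrt(4/56 + shift²). The unexposed subset has SE sqrt(4/50.4) = 0.282 at f = 10% and sqrt(4/42) = 0.309 at f = 25%.

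- Unadjusted, intent-to-treat is 0.268-0.295, slightly closer throughout.
- The plan adjusts for the baseline score. With baseline correlation r (not given), each variance is multiplied by 1 − r². At f = 25%, s = 100%, r = 0.6, the RMSEs are 0.248 and 0.247; at r = 0.7, 0.228 and 0.220, in favour of the subset.

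Neither is uniformly better, and the differences are small.

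**6. Would an arm-by-exposure test help?** Its unadjusted SE is sqrt(4/(56f) + 4/(56(1 − f))) = 0.891 at f = 10% and 0.617 at f = 25%. Power at two-sided 5% is 9-13% for s = 100% and 6-7% for s = 50%. With r = 0.6, f = 25% and s = 100% it is 17%. Such a test would tell the team almost nothing.

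**7. Pilot against trial.** The pilot result is a change in PHQ8. The trial's primary outcome is cognitive impairment. The Interventions section puts the coaches' training in cognitive rehabilitation in the future tense, so the trial version of the app arm appears to contain something the pilot did not. A poor depression response in the pilot is not failure of the trial intervention on cognition, and the range for s in step 3 has no support in the documents.

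**The case for a change.** The strongest case for a change is that the remedy costs little and the text really is silent. The clinic is the same, pilot patients are not ruled out, and the overlap, if any, would fall in the stratum with a directional dCBT hypothesis. Aim 1 results feed later decisions, so their users should know which population the effect describes. Baseline history is also easiest to collect before enrolment starts.

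The factual part of this stands: one history is screened, the other is not, and no record is planned in the text. What does not follow is that the plan is wrong. A drug and an app need not share eligibility rules, and admitting previously treated patients is a legitimate choice in a trial embedded in care. Matching the criteria would trade a wider population for a narrower one; under the step 3 assumptions it would mean replacing 0.10 × 56 = 5.6 to 0.25 × 56 = 14 patients.

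The silence is also weak evidence. The document is a short project summary that does not itemise all baseline data. The registry collects clinical data, and "RxWell is a mobile app, developed and housed at UPMC Health Plan, with health coaches employed by UPMC", so earlier app use can probably be retrieved, although the text does not say so.

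**Conclusion.** The observation is accurate but calls for no change. Earlier exposure precedes randomisation, so it cannot bias the comparison between arms; it affects only whom the average effect describes. Intent-to-treat in the patients actually enrolled remains the right primary analysis with or without an exposure record. An unexposed-only analysis would be a less precise addition, and an interaction test would have little power.

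Under the stated assumptions (stratum of 56, 0.5 SD effect, 10-25% exposed, 50-100% of effect lost) the shift is 0.025-0.125 SD, at most about half of one unadjusted standard error. With baseline adjustment at r = 0.6 the SE is 0.267 × sqrt(1 − 0.36) = 0.214, and the upper ratio becomes 0.125/0.214 = 0.58. A larger overlap would give a larger shift, but none is indicated, and both the amount and the sign are unknown. Saying whether pilot patients enrolled, and tabulating prior exposure to both treatments by arm and depression stratum, is sensible reporting that analysts can supply from treatment history. It is a gap in detail, not a defect in the design or analysis.

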#### **Interventions:**

1. RxWell is a mobile application that consists of CBT techniques and a health coach who provides in-app guidance and risk mitigation. Coaches will receive training to provide cognitive rehabilitation tips. Usage will be tracked.
2. Standardized dosing of amphetamine/dextroamphetamine monitored monthly with response-based titration to maximum dose of 20 mg bid with side effects tracked. To date, patients with post-COVID fog have tolerated stimulants well.

Clinical flow and recruitment rates for registry study make 12-month recruitment completion feasible.

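### Side-effect tracking is specified for the stimulant arm only, so drug side effects may not be separable from background Long-COVID symptoms

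*Combined protocol and SAP*

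**What the plan says.** The Interventions section describes the two arms one after the other.

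- **Stimulant:** treatment is "monitored monthly with response-based titration to maximum dose of 20 mg bid", and the sentence ends "with side effects tracked". No instrument, grading or attribution rule is given.
- **dCBT:** the app comes with "a health coach who provides in-app guidance and risk mitigation", and then "Coaches will receive training to provide cognitive rehabilitation tips. Usage will be tracked". Side effects and adverse events are not mentioned.

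The Methodology paragraph in Summary of Project sets a schedule with no arm restriction: "Participants will complete computerized neurocognitive assessments and other study measures at baseline, 1.5 (interim) and 3 months after randomization".

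The section headed Primary outcome: Cognitive impairment lists three cognitive tests. Its secondary outcomes are the PHQ8, life satisfaction, disability, and ED and outpatient visits. It names no safety or tolerability outcome and no between-arm safety analysis. COVID symptom characteristics enter the multivariable models as covariates.

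**The concern.** The Project Summary defines these patients by symptoms that persist after the acute infection. Complaints that resemble drug side effects can therefore be expected in some of them on any treatment. A count of such complaints in the stimulant arm mixes drug effect with background illness. Randomisation can separate the two only if both arms are asked the same questions at the same times.

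The contact schedule adds a second imbalance. Stimulant patients are monitored monthly, while the assessments shared by both arms fall at baseline, 1.5 and 3 months. Even if complaints in the dCBT arm were noted informally, stimulant patients would have more occasions to report.

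At stake is what the trial can say about harm. It would give a randomised comparison of efficacy beside an uncontrolled account of side effects. The evidence cited so far, that clinic patients have tolerated stimulants well, also has no comparator. A randomised trial is the place to supply one.

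**Working it through.** **1. Is there a figure to reproduce?** No. The documents state no side-effect rate, safety target, significance level or power. The check is a comparison of texts, followed by an illustration on stated assumptions.

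**2. What is recorded in each arm, as written**

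| Item | Stimulant | dCBT |
|---|---|---|
| Side effects | Tracked | Not mentioned |
| Contact specific to the arm | Monthly monitoring | Coach, in the app |
| App usage | Not applicable | Tracked |
| PHQ8, life satisfaction, disability | Yes | Yes |
| ED and outpatient visits | Yes | Yes |
| Adverse-event or tolerability outcome | None | None |

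The shared rows would show worsening mood, loss of function, and events serious enough to lead to a visit. They would not show a symptom that a patient tolerates without seeking care. The coach's role is not described as producing a record that could be set against the stimulant arm's.

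**3. Inputs for the illustration**

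- Sample size (Project Summary): "We plan to study 120 post-COVID patients seen in the Long-COVID clinic over the next 12 months".
- Allocation (Methodology): patients are "assigned with a 1:1 allocation to either arm using a permuted block design stratified by depression severity", so 120 / 2 = 60 per arm.
- Background rate b, the share of patients reporting a given symptom within 3 months whatever the treatment: **assumed**, 10% to 40%.
- Two-sided significance level 0.05 and a true excess of 20 points for the power column: **assumed**.
- Every randomised patient contributes: **assumed**; losses would widen the intervals.

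**4. Formulas**

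- Background reports expected in the stimulant arm if the drug causes none: 60 × b.
- 95% half-width for the between-arm difference, with equal true rates and the same record in both arms: 1.96 × √(2b(1 − b)/60). At b = 0.20 this is 1.96 × √(0.32/60) = 1.96 × 0.0730 = 0.143.
- Power for a true excess of 0.20, by the normal approximation with the pooled variance under the null: Φ[(0.20 − 1.96 × √(2p̄(1 − p̄)/60)) / √((p₁(1 − p₁) + b(1 − b))/60)], where p₁ = b + 0.20 and p̄ = b + 0.10. At b = 0.20 this is Φ[(0.20 − 0.164)/0.0816] = Φ(0.44) = 0.67.

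**5. Results**

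| Assumed b | Background reports among 60 | Half-width, same record in both arms | Power for a true 20-point excess |
|---|---|---|---|
| 10% | 6 | 10.7 points | 79% |
| 20% | 12 | 14.3 points | 67% |
| 30% | 18 | 16.4 points | 61% |
| 40% | 24 | 17.5 points | 59% |

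**6. Reading.** The second column shows how many reports could arise with no drug effect at all. It does not estimate a bias in any planned analysis. With a stimulant-only record, the excess over background cannot be estimated at any value of b. With a common record it can be, with only moderate precision.

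**The case against.** The strongest reply is that this is a short, proposal-style document and that the asymmetry is inferred from silence. The side-effect phrase closes a sentence on dosing, monitoring and titration, and can be read as ordinary oversight of a titrated drug. "Usage will be tracked" reads as a statement about adherence. Nothing says that events in the dCBT arm will go unrecorded, or that the Interventions section is the whole safety plan. This stands as a limit on the claim: the documents do not show an intention to collect harms in one arm only. It does not supply the missing record, because no other section describes a common one.

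A reader might infer several stronger points that the documents do not support.

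- **That the dCBT arm records nothing but app usage.** The coach's risk-mitigation role and the shared outcomes contradict this.
- **That deteriorating mood on dCBT would be missed.** The PHQ8 is a secondary outcome with no arm restriction. It is not given its own schedule, but it falls naturally among the study measures taken at baseline, 1.5 and 3 months.
- **That a spurious 20- to 40-point excess would be reported against the stimulant.** That figure merely restates an assumed background rate and scores uncollected dCBT data as zero events. No planned analysis does so. No attribution rule is given, and the Phase 3 graduation rules are not described as using side effects.
- **That equal collection would make the comparison unbiased.** One arm takes a drug, the other uses an app, and no blinding is described. Expectation, and prompting at monthly visits, could still affect reporting.

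**Conclusion.** The point holds as a gap in what the trial will collect. Side-effect tracking is specified for the stimulant arm only, and no adverse-event or tolerability outcome is defined for either arm. Mood, disability and health-care visits allow a partial, non-specific comparison, but no side-effect record is common to both arms. Side effects seen on stimulant may therefore not be distinguishable from background Long-COVID symptoms.

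The size is unknown, because the documents give no background rate. The direction and amount of any misattribution are also open, since no attribution rule is stated. The precision quoted for a common record, about 14 to 18 points either way, rests on 60 per arm with complete data and an assumed background rate of 20% to 40%. It describes what the remedy would deliver and is not a measure of present error. The planned efficacy analyses are not affected.

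**What to change.** State in the Interventions and Methodology text that the same symptom and adverse-event checklist, worded identically, is completed in both arms at the existing baseline, 1.5- and 3-month assessments. The baseline round matters most, because it identifies symptoms present before treatment and cannot be recovered later.

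In the statistical analysis text, add a safety summary that reports between-arm differences with 95% confidence intervals. List events found only at monthly stimulant monitoring separately, outside that comparison. Note beside the table that, with no blinding described, differential reporting may remain.

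If common collection is already intended, a sentence saying so, with the instrument and schedule, settles most of the point.

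The cost is a few minutes of participant time per assessment and one extra table. No visit is added, and no dose or clinical rule changes.
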